8.3.3.3 EXPECTEDNESS

The investigator will be responsible for determining whether an adverse event (AE) is expected or unexpected. An AE will be considered unexpected if the nature, severity, or frequency of the event is not consistent with the risk information previously described for the study intervention.

8.3.4 TIME PERIOD AND FREQUENCY FOR EVENT ASSESSMENT AND FOLLOW-UP

The occurrence of an adverse event (AE) or serious adverse event (SAE) may come to the attention of study personnel during study visits of a study participant presenting for medical care, or upon review by a study monitor.

All AEs including local and systemic reactions not meeting the criteria for SAEs will be captured on the appropriate case report form (CRF). Information to be collected includes event description, time of onset, clinician's assessment of severity, relationship to study product (assessed only by those with the training and authority to make a diagnosis), and time of resolution/stabilization of the event. All AEs occurring while on study must be documented appropriately regardless of relationship. All AEs will be followed to adequate resolution.

Any medical condition that is present at the time that the participant is screened will be considered as baseline and not reported as an AE. However, if the study participant's condition deteriorates at any time during the study, it will be recorded as an AE.

Changes in the severity of an AE will be documented to allow an assessment of the duration of the event at each level of severity to be performed. AEs characterized as intermittent require documentation of onset and duration of each episode.

The study clinician will record all reportable events with start dates occurring any time after informed consent is obtained until 7 (for non-serious AEs) or 30 days (for SAEs) after the last day of study participation. At each study visit, the investigator will inquire about the occurrence of AE/SAEs since the last visit. Events will be followed for outcome information until resolution or stabilization.]

8.3.5 ADVERSE EVENT REPORTING

Details of all adverse events reported spontaneously by subjects or observed by the investigator or study clinician will be recorded in appropriate adverse event report forms and reported to the principal investigator and the responsible medical doctor. All adverse events observed will be recorded separately.

8.3.6 SERIOUS ADVERSE EVENT REPORTING

The study clinician will immediately report to the sponsor any serious adverse event, whether or not considered study intervention related, including those listed in the protocol or investigator brochure and must include an assessment of whether there is a reasonable possibility that the study intervention caused the event. Study outcome variables that are serious adverse events (e.g., all-cause mortality) must be reported in accordance with the protocol unless there is evidence suggesting a causal relationship between the study intervention and the event (e.g., death from anaphylaxis). In that case, the investigator must immediately report the event to the sponsor.

All serious adverse events (SAEs) will be followed until satisfactory resolution or until the site investigator deems the event to be chronic or the participant is stable. Other supporting documentation of the event may be requested by the Data Coordinating Center (DCC)/study sponsor and should be provided as soon as possible.

As per C.05.014 (1) of the FDR, the study sponsor will be responsible for notifying FDA/Health Canada/CCMO (Netherlands) of any unexpected fatal or life-threatening suspected adverse reaction as soon as possible, but in no case later than 7 calendar days after the sponsor's initial receipt of the

information. Within 8 days after having initially informed FDA/Health Canada/CCMO of the fatal or life-threatening SAE, the sponsor will submit as complete a report as possible. Follow-up reports of fatal or life-threatening reactions must include an assessment of the importance and implication of the findings, including relevant previous experience with the same or similar drugs.

Where the SAE is neither fatal nor life-threatening, the sponsor will inform FDA/Health Canada/CCMO (Netherlands) within 15 days after becoming aware of the information.

SUSAR's that have occurred in all participating countries should be reported by the sponsor. Further steps will be taken according to local legislation.

8.3.7 REPORTING EVENTS TO PARTICIPANTS

Participants will be notified directly by a study staff member.

8.3.8 EVENTS OF SPECIAL INTEREST

Not applicable

8.3.9 REPORTING OF PREGNANCY

If a participant becomes pregnant while taking the antibiotic intervention, they will discontinue and will be withdrawn from the study.

Animal reproduction studies have been performed in rats and mice at doses up to moderately maternally toxic dose concentrations (i.e., 200 mg/kg/day) (2-4 times the human daily dose) and no evidence of harm to the fetus due to azithromycin was found.³⁹ Reproduction studies for metronidazole have been performed in rates, rabbits, and mice at doses similar to the maximum recommended human dose and have found no evidence of harm to the fetus due to metronidazole.⁴⁰ However, there are no adequate or well-controlled studies of azithromycin or metronidazole use in pregnant women.

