Infection: There have been case reports of sometimes fatal opportunistic infections in patients receiving methotrexate therapy for neoplastic and non-neoplastic diseases. *Pneumocystis carinii* pneumonia was the most common opportunistic infection. There have also been reports of infections, pneumonia, Cytomegalovirus infection, including cytomegaloviral pneumonia, sepsis, fatal sepsis, nocardiosis; histoplasmosis, cryptococcosis, Herpes zoster, *H. simplex* hepatitis, and disseminated *H. simplex*.

Musculoskeletal System: stress fracture.

Ophthalmic: conjunctivitis, serious visual changes of unknown etiology.

Pulmonary System: respiratory fibrosis, respiratory failure, alveolitis, interstitial pneumonitis deaths have been reported, and chronic interstitial obstructive pulmonary disease has occasionally occurred.

Skin: erythematous rashes, pruritus, urticaria, photosensitivity, pigmentary changes, alopecia, ecchymosis, telangiectasia, acne, furunculosis, erythema multiforme, toxic epidermal necrolysis, Stevens-Johnson syndrome, skin necrosis, skin ulceration and exfoliative dermatitis

Urogenital System: severe nephropathy or renal failure, azotemia, cystitis, hematuria, proteinuria; defective oogenesis or spermatogenesis, transient oligospermia, menstrual dysfunction, vaginal discharge, and gynecomastia; infertility, abortion, fetal death, fetal defects.

Other rarer reactions related to or attributed to the use of methotrexate such as nodulosis, vasculitis, arthralgia/myalgia, loss of libido/impotence, diabetes, osteoporosis, sudden death, lymphoma, including reversible lymphomas, tumor lysis syndrome, soft tissue necrosis and osteonecrosis. Anaphylactoid reactions have been reported.

Blood Draws: Phlebotomy can cause discomfort, bruising, a small risk of infection, or thrombosis. Standard aseptic technique will be employed to prevent infection. All blood draws will take place at the time of routine blood test monitoring. The volume of blood required to perform the clinical tests described in this study is 5 ml. A total of 30 ml is expected to be collected over the 52-week study period. These volumes are well below the recommended blood draw volume limits for pediatric study participants—5 ml/kg in a single day and 9.5 ml/kg over an 8 week period—as described by NIH guidelines.

Stool Sample: There is no specific risk to the subject in obtaining a stool sample though bringing a stool sample from home may be inconvenient.

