7 STUDY INTERVENTION DISCONTINUATION AND PARTICIPANT DISCONTINUATION/WITHDRAWAL

7.1 DISCONTINUATION OF STUDY INTERVENTION

Discontinuation of the antibiotic treatment between weeks 4 and 12 does not mean discontinuation of the study. A participant who discontinues the antibiotic intervention will be moved into the Group A control group (Group A1) and receive SOC, but these patients will not be included in the analysis of Group A1 to avoid selection bias as a patient who discontinues treatment in week 11 may differ from a patient who discontinued in week 5. Any patients discontinuing treatment will therefore be reported separately.

The remaining study procedures should be completed as indicated by the study protocol. If a clinically significant finding is identified (including, but not limited to changes from baseline) after enrollment, the investigator or qualified designee will determine if any change in participant management is needed. Any new clinically relevant finding will be reported as an adverse event (AE). Specific criteria for discontinuation due to known or potential AE associated with the study intervention are provided in section 7.2.

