7.2 PARTICIPANT DISCONTINUATION/WITHDRAWAL FROM THE STUDY

Participants are free to withdraw from participation in the study at any time for any reason if they wish to do so without any consequences. An investigator may discontinue or withdraw a participant from the study for the following reasons:

- Pregnancy
- Significant study intervention non-compliance
- Occurrence of a clinical AE known to be associated with study intervention including new onset peripheral neuropathy, new onset seizures, new onset clinically significant leukopenia, new-onset QT prolongation, evidence of hepatotoxicity, allergic reaction. Criteria for stopping investigational therapy due to potential hepatotoxicity include any of the following laboratory abnormalities:
 - ALT or AST >8xULN
 - ALT or AST >5xULN for more than 2 weeks
 - ALT or AST >3xULN and (TBL >2xULN or INR >1.5)
 - ALT or AST >3xULN with the appearance of fatigue, nausea, vomiting, right upper quadrant pain or tenderness, fever, rash, and/or eosinophilia (>5%)

Should any of these laboratory abnormalities occur, the participant will discontinue investigational therapy and undergo appropriate evaluation for other causes of abnormal liver function tests. The participant must be followed until resolution or stabilization and the results of the evaluation for alternate causes of abnormal liver enzymes will be documented in the Reason for Withdrawal Case Report Form (CRF)

- If any other clinical adverse event, laboratory abnormality, or other medical condition or situation occurs such that continued participation in the study would not be in the best interest of the participant
- Disease progression which requires discontinuation of the study intervention
- If the participant meets an exclusion criterion (either newly developed or not previously recognized) that precludes further study participation

The reason for participant discontinuation or withdrawal from the study will be recorded on the Reason for Withdrawal CRF. Subjects who withdraw during the pilot study will try to be replaced.

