8.3.2 DEFINITION OF SERIOUS ADVERSE EVENTS (SAE)

An adverse event (AE) or suspected adverse reaction is considered "serious" if, in the view of either the investigator or sponsor, it results in any of the following outcomes: death, a life-threatening adverse event, inpatient hospitalization or prolongation of existing hospitalization, a persistent or significant incapacity or substantial disruption of the ability to conduct normal life functions, or a congenital anomaly/birth defect.

Important medical events that may not result in death, be life-threatening, or require hospitalization may be considered serious when, based upon appropriate medical judgment, they may jeopardize the

participant and may require medical or surgical intervention to prevent one of the outcomes listed in this definition.

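### A participant who becomes pregnant on the antibiotic is withdrawn and SAE recording closes 30 days later, so a birth defect found at delivery is outside required safety capture

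*Combined protocol and SAP*

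**What the plan says.** Three sections bear on whether a pregnant participant stays in the study.

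- Section 8.3.9 (Reporting of Pregnancy) is mandatory for pregnancy on the antibiotic: "If a participant becomes pregnant while taking the antibiotic intervention, they will discontinue and will be withdrawn from the study". Despite its title it gives no report form, no timeline and no follow-up of the pregnancy or the newborn.
- Section 7.2 is permissive: "An investigator may discontinue or withdraw a participant from the study for the following reasons", with pregnancy first in the list that follows.
- Section 7.1 gives the general rule: "Discontinuation of the antibiotic treatment between weeks 4 and 12 does not mean discontinuation of the study". It asks for the remaining procedures to be completed and points to 7.2 for specific criteria.

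Three more set what is recorded.

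- Section 8.3.4 records events by start date, from consent "until 7 (for non-serious AEs) or 30 days (for SAEs) after the last day of study participation".
- Events already recorded are followed up. Section 8.3.4 says "Events will be followed for outcome information until resolution or stabilization", and 8.3.6 says "All serious adverse events (SAEs) will be followed until satisfactory resolution" or until the event is judged chronic or the participant stable.
- Section 8.3.2 closes its list of serious outcomes with "or a congenital anomaly/birth defect".

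On fetal risk, 2.3.1 lists "infertility, abortion, fetal death, fetal defects" among the methotrexate reactions, and 8.2 gives methotrexate's possible effects on the embryo as the reason for pregnancy tests. For azithromycin and metronidazole, 8.3.9 reports no fetal harm in animal studies and no adequate studies in pregnant women. Section 4.1 recommends methotrexate as maintenance therapy but does not make it a condition of taking part.

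**The concern.** The protocol foresees fetal exposure: it tests, counsels and lists the risk. Yet its one mandatory instruction on pregnancy removes the participant from the study, which starts a 30-day clock on SAE recording. A defect first seen at birth would then start long after the clock has stopped. The protocol defines that outcome as serious but has no rule that leads anyone to ask about it.

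Two smaller losses follow. A randomised participant who is withdrawn has no week-52 status, so under 9.4.1 her missing categorical outcome is imputed as non-response in the ITT comparison. She also counts against completion of the one-year endpoint, which the Netherlands addendum (section 12) makes a feasibility outcome.

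The wording matters beyond the pilot. The addendum says that, if feasibility is adequate, the protocol goes forward without substantial change and pilot data may be included in the full-scale trial, so the gap would go with it.

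**Working it through.** The plan states no figure on this point, so there is none to reproduce. The check is a comparison of rules and some calendar arithmetic.

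**Does another rule fill the gap?** Section 8.3.8 (events of special interest) is marked not applicable. Sections 8.3.4 and 8.3.6 follow only events already recorded, and pregnancy is not defined as an AE or SAE. Section 8.4.2 (unanticipated problems) runs from the investigator becoming aware, and does not require anyone to ask. No section requires follow-up to the outcome of a pregnancy.

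**Inputs from the documents.** Antibiotics run from week 4 to week 12 (4.1). SAE capture extends 30 days, or 30/7 = 4.3 weeks, past the last day of participation (8.3.4). Planned participation is 52 weeks (1.1).

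**Assumptions not in the documents.** Conception to birth takes 38 weeks (range 35 to 40). Pregnancy is detected 2 to 8 weeks after conception. Withdrawal falls on the day of detection and counts as the last day of participation.

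**When capture closes.** Closure = withdrawal week + 4.3.

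- Withdrawal at week 4: 4 + 4.3 = week 8.3.
- Withdrawal at week 12: 12 + 4.3 = week 16.3.

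**Gap from closure to birth.** Gap = (weeks from conception to birth) − (weeks from conception to detection) − 4.3. The conception week cancels out.

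| Conception to birth | Detected at 2 weeks | Detected at 8 weeks |
|---|---|---|
| 35 weeks | 28.7 | 22.7 |
| 38 weeks | 31.7 | 25.7 |
| 40 weeks | 33.7 | 27.7 |

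At 38 weeks the gap is about 26 to 32 weeks, and over the whole range about 23 to 34. Birth is outside the window in every cell.

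**If she stayed in follow-up to week 52.** Capture would close at 52 + 4.3 = week 56.3. Conception as late as week 12 gives birth at 12 + 38 = week 50 (week 52 at 40 weeks), inside the window. The latest conception still covered is 56.3 − 38 = week 18.3 (16.3 at 40 weeks, 21.3 at 35 weeks). Later conceptions need a separate contact. They span 52 − 18.3 = 33.7 of the 52 weeks, so they are not a marginal part of the period if the rule applies throughout.

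**The case against.** The strongest case on the other side has four parts.

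**The listed fetal harm is not the antibiotics'.** This stands. Abortion, fetal death and fetal defects are listed under methotrexate, and a physician may continue azathioprine instead. The listed harm reaches a participant on the antibiotic only if she also takes methotrexate. The gap does not depend on it, because 8.3.2 makes a congenital anomaly serious whatever the exposure.

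**The harm would not necessarily go unrecorded.** A reader might infer that it could never be recorded, or would be reported as absent. The documents do not support that. A pregnancy loss within 30 days of withdrawal would still be captured if judged serious, and then followed; 8.3.2 names congenital anomaly but not abortion or fetal death. The start date of an anomaly is open to interpretation. Later voluntary reporting is not forbidden. Section 7.2 puts the reason for withdrawal on a CRF, so the pregnancy would be documented and its outcome unknown.

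**Section 7.1 is a general rule with an exception.** Largely true. Section 7.1 refers to 7.2, and 7.2 names pregnancy, so 8.3.9 can be read as a specific exception to 7.1. The clearer mismatch is between 7.2, where withdrawal is permitted, and 8.3.9, where it is required.

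**The event is improbable.** This also stands. Pregnancy is an exclusion criterion, post-menarchal girls starting methotrexate are tested at screening and week 4, counselling is repeated at every visit, and the trial enrols 20 children of both sexes aged 3 to 17. The efficacy consequence is slight too, since the addendum concedes that the numbers cannot support efficacy conclusions. This lowers the priority but does not supply the missing rule.

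**Conclusion.** The point holds in a limited form. Required withdrawal in 8.3.9, the 30-day limit in 8.3.4 and the lack of any pregnancy-outcome follow-up together mean that the protocol does not require a birth defect found at delivery to be recorded. Under the assumptions above, delivery comes about 26 to 32 weeks after capture closes. No combination of assumptions tried brings it inside the window.

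The mandatory rule covers only pregnancy while taking the antibiotic. Pregnancy in groups A1 or B, or after week 12, falls under the optional rule in 7.2, and there too no outcome follow-up is specified.

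Severity is low because the event is unlikely. It is still worth correcting, because the gap comes from a stated rule, concerns an outcome the protocol itself calls serious, and would pass into the larger trial.

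**What to change.** Reconcile 7.1, 7.2, 8.3.4 and 8.3.9 so that pregnancy in any group, at any time in the 52 weeks, does not end safety data collection. Whether and when treatment stops is for the sponsor to settle; nothing here bears on it. The revised text should say that:

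- with the participant's consent, follow-up continues on the existing visit schedule to week 52;
- the pregnancy outcome is recorded on the AE/SAE form;
- that outcome is exempt from the 30-day limit;
- if she was randomised, she stays in the ITT set with her observed week-52 status.

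The cost is wording in 8.3.9, 7.2 and 8.3.4. No new visit is needed when delivery falls by week 56.3, that is, for conceptions up to about week 18 (16 to 21 over the assumed range). For later conceptions, one further contact after delivery is enough.

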8.4 UNANTICIPATED PROBLEMS

8.4.1 DEFINITION OF UNANTICIPATED PROBLEMS (UP)

The Office for Human Research Protections (OHRP) considers unanticipated problems involving risks to participants or others to include, in general, any incident, experience, or outcome that meets all of the following criteria:

- Unexpected in terms of nature, severity, or frequency given (a) the research procedures that are described in the protocol-related documents, such as the Institutional Review Board (IRB)-approved research protocol and informed consent document; and (b) the characteristics of the participant population being studied;

- Related or possibly related to participation in the research (“possibly related” means there is a reasonable possibility that the incident, experience, or outcome may have been caused by the procedures involved in the research); and
- Suggests that the research places participants or others at a greater risk of harm (including physical, psychological, economic, or social harm) than was previously known or recognized.

8.4.2 UNANTICIPATED PROBLEM REPORTING

The investigator will report unanticipated problems (UPs) to the reviewing Institutional Review Board (IRB) and to the Data Coordinating Center (DCC)/lead principal investigator (PI). The UP report will include the following information:

- Protocol identifying information: protocol title and number, PI’s name, and the IRB project number;
- A detailed description of the event, incident, experience, or outcome;
- An explanation of the basis for determining that the event, incident, experience, or outcome represents an UP;
- A description of any changes to the protocol or other corrective actions that have been taken or are proposed in response to the UP.

To satisfy the requirement for prompt reporting, UPs will be reported using the following timeline:

- UPs that are serious adverse events (SAEs) will be reported to the IRB and to the DCC/study sponsor within 7 calendar days of the investigator becoming aware of the event.
- Any other UP will be reported to the IRB and to the DCC/study sponsor within <insert timeline in accordance with policy> of the investigator becoming aware of the problem.
- All UPs should be reported to appropriate institutional officials (as required by an institution’s written reporting procedures), the supporting agency head (or designee), and the Office for Human Research Protections (OHRP) within <insert timeline in accordance with policy> of the IRB’s receipt of the report of the problem from the investigator.

8.4.3 REPORTING UNANTICIPATED PROBLEMS TO PARTICIPANTS

Participants will be notified directly by a study staff member.

9 STATISTICAL CONSIDERATIONS

9.1 STUDY OUTCOME VARIABLES

The primary outcome evaluation:

The primary efficacy outcome variable is being in sustained remission defined as PCDAI ≤ 10 at 52 weeks from start of therapy AND without steroid dependence and without the need for repeat induction therapy, anti-TNF α , or surgery by 52 weeks from start of therapy.

The secondary outcome evaluations at each study visit include:

- Mean change in PCDAI score from baseline to weeks 4, 12, 24, 36, and 52.
- Mean change in Inflammatory markers: CRP and fecal calprotectin from baseline to weeks 4, 12, 24, 36, and 52.
- Mean change in PRO score (IMPACT questionnaire) from baseline to weeks 4, 12, 24, 36, and 52.
- Improvement (yes vs no) of disease activity (change in PCDAI < 0) rate at weeks 4, 12, 24, 36, and 52.
- Improvement (yes vs no) of C-Reactive Protein (change in CRP < 0 mg/dL) and fecal calprotectin (change in FCP < 0 µg/g) rate at weeks 4, 12, 24, 36, and 52.
- Normalization (yes vs no) of disease activity (PCDAI < 10) rate at weeks 4, 12, 24, 36, and 52.
- Normalization (yes vs no) of C-Reactive Protein (CRP; < 0.5 mg/dL) and fecal calprotectin (FCP; < 250 µg/g) rate at weeks 4, 12, 24, 36, and 52.

